### **9.3.24 Prior, Concomitant and Post treatment Medications**

A prior medication is considered to be any medication that is taken within a year prior to the first randomized, double-blind study drug dosing.

A concomitant medication (CM) is considered to be any medication with start dates or stop dates within the Treatment Period. Specifically, CMs are medications: that are continued from Screening and continued after the first double-blinded study drug dosing; with start dates within the first dose date through last dose date + 24 hours; with end dates within the first dose date through last dose date + 24 hours; having a missing CM end date, or ongoing).

Post medications are considered to be any medication: taken after the last study drug dose date + 24 hours, having a missing CM end date, or ongoing.

### **9.3.24.1 Prohibited Concomitant Medications**

Prohibited and cautionary concomitant medications are those medications with their potential for metabolic interactions with tildacerfont. Specific definitions can be found in Protocol Sections 6.5.2 and 13.1. Appendix 13.1 in the protocol provides a non-exhaustive list of medications.

### **9.3.25 Adverse Events**

AEs are those AEs with onset date from the signing of the ICF until the end of the follow up period.

Treatment-emergent adverse events (TEAEs) are defined as any AEs, regardless of relationship to study drug, that have an onset or worsening in severity on or after the first dose of double-blinded study drug (within Treatment Period) until 30 days after the final dose of study drug (safety follow-up visit).

If a subject discontinues study drug but remains in the study, AEs with onset date after 30 days of last dose of study drug until the end of the follow up period will be considered post-treatment adverse events.

Related TEAEs are those reported by investigators as possibly related, probably related, or definitely related to the study drug.

AESIs are events that must be monitored on an ongoing basis as defined in Protocol Section 8.3.8 and identified in the AE eCRF page. The AESIs that are serious AEs (SAEs) will be handled according to guidelines from the National Cancer Institute Common Terminology Criteria for Adverse Events (CTCAE 2017) version 5.0, as described in Protocol Section 8.3.3.1.

### **9.3.26 Glucocorticoid Therapy**

GC therapies are concomitant medications as collected in the Prior & Concomitant Daily Glucocorticoids/Mineralocorticoids eCRF form.

### 9.3.26.1 Glucocorticoid Dose in Hydrocortisone Equivalents

[Table 8](#) defines the potencies of various GCs relative to HC in treating CAH, as pre-specified and provided by the Sponsor. These conversion factors will be used to standardize and determine whether a subject's daily GC dose satisfies study eligibility criteria and provide general guidelines for GC tapering in Part C.

**Table 8 Relative Potencies of Glucocorticoids in Hydrocortisone Equivalents**

Glucocorticoid	Potency in CAH (HCe)
Hydrocortisone	1
Prednisone	4
Prednisolone	5
Methylprednisolone	5
Fludrocortisone	0
Dexamethasone	70
Cortisone Acetate	0.8

### 9.3.26.2 Glucocorticoid Total Daily Dose in Hydrocortisone Equivalents

Since a subject may be taking more than one dose (Morning, Midday, Midday 2, and/or Evening) of more than one GC medication, the total daily GC dose of a given subject at a given day is calculated as the sum of doses in HCe per day of concomitant GC therapies, excluding stress dosing.

### 9.3.26.3 Stress Event

A stress event is defined as an entry in the diary indicating a stress dose was taken. Consecutive days of stress dosing are counted as a single stress event.

### 9.3.26.4 Baseline Glucocorticoid Dose

Based on the GC therapies collected in the Prior & Concomitant Daily Glucocorticoids/Mineralocorticoids, the baseline GC dose is the GC Total Daily Dose in HCe at Treatment Study Day 1.

### **9.3.26.5 Glucocorticoid BSA Based Dose**

The baseline GC BSA-based dose is calculated as the GC dose ([Section 9.3.26.5](#)) divided by the body surface area ([Section 9.3.9](#)) at the corresponding time point, rounded to two decimal places.

### **9.3.26.6 Glucocorticoid Dose at Visit**

Based on the GC therapies collected in the Prior & Concomitant Daily Glucocorticoids/Mineralocorticoids, GC dose at visit is calculated as the sum of the total daily dose in HCe of all concomitant GC therapies at the date of visit as collected in the Date of Visit eCRF.

### **9.3.26.7 Change in Glucocorticoid Dose and A4 $\leq$ ULN**

A change in GC dose meeting A4  $\leq$  ULN criterion is defined as follows:

GC dose change is calculated as the sum of the total daily dose in HCe of all concomitant GC therapies at Visit subtracted by the Baseline GC Dose.

If at Visit X A4  $\leq$  ULN, the GC dose change is recorded as observed. If at Visit X A4  $>$  ULN, the GC dose change at the visit is recorded as missing.

## **9.3.27 Variables Related to Menstrual Cycles**

### **9.3.27.1 Length (Days) of a Menstrual Cycle**

Menstrual cycle length is calculated as (LASTDAY – FIRSTDAY + 1 day), where FIRSTDAY is the date of the first day in a menstrual cycle where the subject records ‘Yes’ they menstruated today, and LASTDAY is the date of the last consecutive day a patient answered ‘Yes’ they menstruated today within the same menstrual cycle.

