8.1.4.4 Menstrual Cyclicity

Female subjects will record menstrual information in their electronic study diaries, including the start and stop dates of menses.

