### **9.3.27.2 Time (Days) Between Menstrual Cycles**

Time (days) between menstrual cycles is calculated as (FIRSTDATEi – LASTDATEi-1 + 1 day), where FIRSTDATEi is the first date of current menstrual cycle and LASTDATEi-1 is the last date of the previous menstrual cycle.

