### 13.5.10 Additional Exploratory Analyses

#### 13.5.10.1 Menstrual Cycle Length

Menstrual cycle length, which is defined in [Section 9.3.27.1](#), will be summarized descriptively by treatment group and scheduled time point. The time between menstrual cycles, which is defined in [Section 9.3.27.2](#), will also be summarized descriptively.

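### SAP 9.3.27 labels duration of menses as menstrual cycle length, and its time-between-cycles formula runs 1 or 2 days too long

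*SAP*

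**What the plan says.** SAP 9.3.27.1: "Menstrual cycle length is calculated as (LASTDAY – FIRSTDAY + 1 day"). Both anchors are diary days on which the subject reported bleeding. The start is defined as follows: "FIRSTDAY is the date of the first day in a menstrual cycle where the subject records" a yes. For the end, "LASTDAY is the date of the last consecutive day a patient answered" yes, within the same cycle.

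SAP 9.3.27.2 ("Time (days) between menstrual cycles is calculated as" …) takes FIRSTDATE(i) − LASTDATE(i−1) + 1 day, where FIRSTDATE(i) "is the first date of current menstrual cycle and LASTDATE"(i−1) is the last date of the cycle before it.

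SAP 13.5.10.1, under Additional Exploratory Analyses, says that cycle length "will be summarized descriptively by treatment group and scheduled time point". It treats the second variable descriptively as well ("The time between menstrual cycles, which is defined in" 9.3.27.2). It specifies no hypothesis test for either.

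On data capture, Protocol 8.1.4.4 states: "Female subjects will record menstrual information in their electronic study diaries, including the start and stop dates of menses". Protocol 4.1.3 has female subjects keep these records up to Week 76.

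**The concern.** A reader will take a table of menstrual cycle length to show the interval from one onset to the next. The SAP variable stops at the end of bleeding, so it measures something else and does not respond to the interval between onsets. No other section of either document gives an onset-to-onset definition.

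The second variable has a smaller problem. Adding one day to the difference between a last bleeding day and the next first bleeding day counts both of those days as part of the time between episodes.

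The stake is modest but real. The protocol names irregular menses and amenorrhea among the effects of androgen excess (Section 2.1), places menstrual cyclicity under hyperandrogenic symptoms (8.1.4.4), and lists changes in it among those investigators must weigh (7.1.6). Programmed as written, the study report would carry a cycle-length table with values of a few days, and a gap table whose means, medians and ranges are shifted.

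**Working it through.** The documents give no numerical result for these variables, so there is no stated figure to reproduce. The check is date arithmetic on the two SAP formulas.

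**Inputs.** The formulas come from SAP 9.3.27.1 and 9.3.27.2. The example is an assumption: bleeding on days 1 to 5, next onset on day 29.

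**Length.**
- SAP: LASTDAY − FIRSTDAY + 1 = 5 − 1 + 1 = 5
- Onset to onset: 29 − 1 = 28

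**Gap.**
- SAP: FIRSTDATE(i) − LASTDATE(i−1) + 1 = 29 − 5 + 1 = 25
- Bleed-free days (days 6 to 28): 29 − 5 − 1 = 23
- Elapsed time (plain date difference): 29 − 5 = 24

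**Reconciliation.** SAP length plus SAP gap is 5 + 25 = 30 for a 28-day cycle. Bleeding days plus bleed-free days is 5 + 23 = 28.

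**General case.** Let L be the onset-to-onset interval and b the number of bleeding days, with bleeding on days 1 to b and the next onset on day L + 1. The SAP length is b, whatever L is. The SAP gap is (L + 1) − b + 1 = L − b + 2, against L − b bleed-free days and L − b + 1 elapsed days. The gap is therefore too long by exactly 2 or exactly 1, and length plus gap is L + 2. A calendar check over cycles of 21 to 60 days with 2 to 9 bleeding days gave the same offsets in every case. Selected rows:

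| Onset to onset | Bleeding days | SAP length | SAP gap | Bleed-free days | Elapsed days | SAP length + gap |
|---|---|---|---|---|---|---|
| 28 | 5 | 5 | 25 | 23 | 24 | 30 |
| 28 | 7 | 7 | 23 | 21 | 22 | 30 |
| 35 | 5 | 5 | 32 | 30 | 31 | 37 |
| 45 | 5 | 5 | 42 | 40 | 41 | 47 |

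**Effect on the summaries.** A constant added to every gap moves the mean, median, quartiles, minimum and maximum by 1 or 2 days. It leaves the SD and interquartile range unchanged and cancels in any difference between arms or over time. The length problem does not cancel, because a different quantity is being summarised.

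**The case against.** The best defence is that SAP 9.3.27 uses the word cycle for a bleeding episode throughout. A time between cycles makes sense only on that usage. The first variable is then an explicitly defined quantity under a poor label, not a miscalculation. The onset-to-onset interval can also be recovered for each pair of episodes as SAP length + SAP gap − 2 (5 + 25 − 2 = 28). This is fair, and it is why the first part is best described as a labelling and definition problem. It does not rescue the planned table, because no onset-to-onset variable is summarised and the label invites the wrong reading.

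On the gap, the SAP never says it counts bleed-free days, and a one-day addition is its usual convention for inclusive durations (9.3.2, 9.3.23.3, 9.3.23.7). The formula is correct as an inclusive count of both end days. But both end days are bleeding days, and such a count is not time between episodes. Nor does it help to read LASTDATE as the day before the next onset: the formula then returns 2 where the gap is 0.

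A reader might go further and infer that these summaries cannot show any drug effect on cyclicity. The documents do not support that. The gap is also summarised, and with 5 bleeding days it takes the values 25, 32 and 42 for 28-, 35- and 45-day intervals. Likewise, regular and irregular cycles give the same SAP length only where bleeding duration is the same, which is a feature of the example. A reader might also infer that a study endpoint is compromised. Menstrual cyclicity is a collected assessment, but it appears neither among the endpoints in Protocol Section 3 nor in SAP Table 1.

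**Conclusion.** The point holds in limited form. The variable that SAP 9.3.27.1 calls menstrual cycle length is duration of menses; this follows from the text and needs no assumption. With the assumed 28-day cycle and 5 bleeding days it reports 5 instead of 28.

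The gap in SAP 9.3.27.2 is too long by 2 days if bleed-free days are meant (25 against 23) or by 1 day if elapsed time is meant (25 against 24). A flat statement of two days would assume the first reading, which the SAP does not spell out. On either reading the shift is constant, so reported values are biased while between-arm differences and spread are not.

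The reach is confined to two descriptive, additional exploratory summaries. No primary, secondary or numbered exploratory analysis is touched. This is a minor correction, worth making before the tables are programmed.

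**What to change.** In SAP 9.3.27:

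- Rename the 9.3.27.1 variable duration of menses and keep its formula.
- Add cycle length = FIRSTDATE(i) − FIRSTDATE(i−1).
- Define the 9.3.27.2 gap as bleed-free days, FIRSTDATE(i) − LASTDATE(i−1) − 1, and say so in words.

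The menses of the earlier episode plus the following gap then equals the cycle length (5 + 23 = 28), which also gives programmers a built-in check. Update SAP 13.5.10.1 so that each summary carries the matching name.

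The cost is SAP derivation wording and the corresponding table labels. Start and stop dates of menses are already collected, so no new data or protocol change is needed.

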### **9.3.27.2 Time (Days) Between Menstrual Cycles**

Time (days) between menstrual cycles is calculated as (FIRSTDATEi – LASTDATEi-1 + 1 day), where FIRSTDATEi is the first date of current menstrual cycle and LASTDATEi-1 is the last date of the previous menstrual cycle.

### 9.3.28 Geographic Regions

About 75 study centers will participate in this study. Three geographic regions will be classified by the countries where these study centers are located: North America, European Union and United Kingdom, and the rest of the world.

## 9.4 Analysis Windows

Analysis visits will match the protocol-specified visits (Screening, Day 1, Week 4, etc.). Unscheduled clinical visits may be used to capture missed or partially completed clinical visits; therefore, analysis visits and their windows are defined using Study Day (See [Section 9.3.2](#)). For the purposes of data analysis and summary, assessments and/or measurements, the protocol-specified visit will be preferentially flagged for analysis. In the absence of a protocol-specified visit, the analysis flag will be based on the collection date/time that is closest to the protocol-scheduled time point (or target Study Day). Analysis visit windows are presented in [Table 9](#).

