11.2 Study Conduct in the Context of COVID-19 or Other Logistical Challenges

All study activities will be conducted in accordance with relevant local, regional, and national guidance around COVID-19.

If in-clinic visits are no longer possible, in-clinic-only activities (eg, scrotal ultrasound) will not be conducted. After a site reopens or the shelter-in-place order is lifted, attempts should be made to conduct any missed in-clinic activities via an unscheduled visit.

If a subject or a member of the subject's household is suspected or confirmed to have COVID-19, the Investigator must consult with the Medical Monitor to determine the best course of action. In this situation, only telemedicine activities can proceed. If the subject misses scheduled study activities during this time, an unscheduled visit will be conducted once the subject or member of his/her household no longer has suspected or confirmed COVID-19. At a minimum, safety labs must be performed at the unscheduled visit. Subjects cannot go more than 3 months or 2 consecutive scheduled visits without labs being drawn.

For scenarios not delineated here or for further clarification, the Investigator should consult with the Medical Monitor to determine the best course of action.

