## 5.2 Study Treatment

### 5.2.1 Study Drug Administration

During the Run-in Period, subjects will take placebo for 6 weeks. In Part A of the study (the first 12 weeks of the Treatment Period), subjects will receive randomized study drug treatment (i.e., tildacerfont 50, 100, or 200 mg QD or matching placebo) without dose escalation. During Part B (the second 12 weeks of the Treatment Period) and Part C (the last 46 weeks of the Treatment Period), all subjects will receive tildacerfont and the dose level will be determined as follows.

- Subjects who were randomized to placebo in Part A will receive 100 mg tildacerfont QD at the beginning of Part B (Week 18).
- Subjects who were randomized to 200 mg tildacerfont QD in Part A will continue to receive tildacerfont at 200 mg QD throughout Parts B and C.
- Based on A4 results from the Week 18 and Week 24 visits, eligible subjects may undergo a tildacerfont dose escalation after each of these study visits. The RTSM system will assign appropriate dose levels of tildacerfont based on subjects' A4 results (i.e., A4  $\leq$  ULN or A4  $>$  ULN) at Weeks 18 and 24. Specifically:

- o Subjects taking tildacerfont 50 mg QD will either continue to receive the same dose (if A4  $\leq$  ULN) or be escalated to 100 mg tildacerfont QD (if A4  $>$  ULN and the subject is tolerating his/her current tildacerfont dose)
  - o Subjects taking 100 mg tildacerfont QD will either continue to receive the same dose (if A4  $\leq$  ULN) or be escalated to 200 mg tildacerfont QD (if A4  $>$  ULN and the subject is tolerating his/her current tildacerfont dose).
- At Week 30, all subjects will be escalated to 200 mg tildacerfont QD.

During the optional Open-Label Extension Period, subjects will continue to receive tildacerfont at 200 mg QD.

Tildacerfont is produced as a 50 mg tablet. The placebo is produced to look identical to the tildacerfont tablet. To maintain the blind, all subjects will receive the same number of study drug tablets, and take 4 tablets a day with the appropriate number of tildacerfont and/or placebo tablets for the assigned. The 200 mg tildacerfont dose will contain 4 tildacerfont tablets in each compartment; the 100 mg tildacerfont dose will contain 2 tildacerfont tablets and 2 placebo tablets; the 50 mg tildacerfont dose will contain 1 tildacerfont tablet and 3 placebo tablets; and the placebo dose will contain 4 placebo tablets.

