### 9.3.10 Baseline Values

Baseline values of serum biomarkers (i.e., A4, 17-OHP, and ACTH) are defined as the average of the Day 1, Week 4 and Week 6 assessments that are on or prior to the date of the first dose of double-blind study drug during Part A, allowing for unscheduled assessments to be windowed and replace missed scheduled visits. Visit windowing conventions will be used to identify the assessments that are used to construct baselines (see [Section 9.4](#)). Day 1 values are defined as the last non-missing assessment up to Day 14 for hormone assessments. For all other parameters, baseline values are defined as the last non-missing assessment prior to the first dose of randomized, double-blind study drug in Part A of the study. The following [Table 3](#) provides a guide for the baselines to use in analysis.

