**Table 9 Analysis Visit Windows (Clinic Visits Only)**

Protocol Specified Visit Number	eCRF Visit Label	Analysis Visit	Target Study Day	Start (days)	Stop (days)
Visit 1a	SCR	Screening	-15	-45	-7
Visit 1b	SCR	Screening	-15	-45	-7
Visit 2	WK0	Day 1	1	-6	14
Visit 3	WK4	Week 4	29	15	36
Visit 4	WK6	Week 6	43	37	57
Visit 5	WK10	Week 10	71	58	85
Visit 6	WK14	Week 14	99	86	113
Visit 7	WK18	Week 18	127	114	148
Visit 8	WK24	Week 24	169	149	190
Visit 9	WK30	Week 30	211	191	239
Visit 10	WK38	Week 38	267	240	295
Visit 11	WK46	Week 46	323	296	365
Visit 12	WK58	Week 58	407	366	449
Visit 13	WK70	Week 70	491	450	512
Visit 14	WK76	Week 76	533	513	575
Visit 15	WK80	Follow-up	Last dose	Last dose +1	Last dose +30
Visit 1 OLE	WK76	Week 76	533	513	575

Protocol Specified Visit Number	eCRF Visit Label	Analysis Visit	Target Study Day	Start (days)	Stop (days)
Visit 2 OLE	WK88	Week 88	617	576	659
Visit 3 OLE	WK100	Week 100	701	660	785
Visit 4 OLE	WK124	Week 124	869	786	953
Visit 5 OLE	WK148	Week 148	1037	954	1121
Visit 6 OLE	WK172	Week 172	1205	1122	1289
Visit 7 OLE	WK196	Week 196	1373	1290	1457
Visit 8 OLE	WK220	Week 220	1541	1458	1625
Visit 9 OLE	WK244	Week 244	1709	1626	1793
Visit 10 OLE	WK268	Week 268	1877	1794	1962
Visit 11 OLE	WK292	Week 292	2046	1963	2130
Visit 12 OLE	WK316	Week 316	2213	2131	
Visit 12 OLE		Follow-up	Last dose	Last dose +1	Last dose +30

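### The SAP's Week 18 window has no cut-off at the first Part B dose, so a late make-up assessment taken after the switch can be analysed as placebo-controlled Week 18 data

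*SAP*

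**What the plan says.** SAP 9.4 sets windows by calendar alone: "analysis visits and their windows are defined using Study Day". Unscheduled visits may stand in for missed or partly completed ones. The scheduled visit has priority; only when there is none does the fallback apply, under which "the analysis flag will be based on the collection date/time that is closest to the protocol-scheduled time point". The Table 9 rows (target, start, stop) are "Visit 7 WK18 Week 18 127 114 148" and "Visit 8 WK24 Week 24 169 149 190".

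Treatment changes inside the first of these windows. SAP 5.2.1 states: "Subjects who were randomized to placebo in Part A will receive 100 mg tildacerfont QD at the beginning of Part B (Week 18"). Subjects on 50 mg or 100 mg whose A4 is above ULN, and who tolerate their dose, are escalated; the 200 mg arm is unchanged. SAP Table 1 nevertheless defines the Week 18 endpoints as measured after 12 weeks of double-blind, placebo-controlled treatment, and SAP 9 summarises Part A by randomised group.

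The SAP does apply a dose-date condition elsewhere. Under SAP 9.3.10, baseline hormone values must be "on or prior to the date of the first dose of double-blind study drug during Part A". SAP 9.3.23.3 can end an exposure period the day before the next period's first dose. Neither rule reaches Week 18 assessments.

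**The concern.** Followed as written, the fallback can place a value taken on tildacerfont in the placebo arm, which pulls the placebo mean towards the active arms. It can also place a value taken on the next dose up in the 50 mg or 100 mg arm. Because Part A output is by randomised group, neither would show in the tables.

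Late values have documented routes. Where clinic visits have not been possible, Protocol 11.2 says that "attempts should be made to conduct any missed in-clinic activities via an unscheduled visit", and it names the scrotal ultrasound as an example of an in-clinic-only activity. SAP 10.2.3 uses a retest when a first sample is invalidated. Week 18 TART volume (SAP 13.5.3) and SF-36 (SAP 13.5.6) are both compared with placebo by randomised arm.

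The treatment-policy statement in SAP 13.3.1 does not settle the matter. It lists the intercurrent events to be disregarded, and the planned move to Part B is not among them.

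**Working it through.** **Where Day 148 comes from.** The midpoint of the Week 18 and Week 24 targets is (127 + 169)/2 = 148, the listed stop day. The same rule reproduces the listed stops for Week 6 (57), Week 10 (85), Week 14 (113), Week 24 (190) and Week 30 (239). The limit was set by visit spacing, without regard to the treatment switch. Day 148 is also the Week 21 telephone contact, which the Protocol 1.3.3 schedule places in Part B.

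**How much of the window follows the switch.**
- Window length: 148 − 114 + 1 = 35 days.
- Days after the planned switch at Day 127: 148 − 127 = 21, or 21/35 = 60%.
- Subjects stay on Part A drug until the A4 result and new supply arrive (Protocol 6.1.2). The delay is not stated. Assuming 3, 7 or 14 days leaves 18, 14 or 7 days, that is 51%, 40% or 20% of the window.

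**Which endpoints are exposed.**
- A4: Part B blister cards are assigned only when the Week 18 A4 value is confirmed (Protocol 1.3.3, footnote 19). A subject on Part B drug should normally already have a Week 18 A4 value, so the fallback is not reached.
- 17-OHP and ACTH: same schedule item and same 8 AM draw as A4 (Protocol 1.3.3, footnotes 5 and 6; 8.1.1). They share the protection unless one analyte fails and is redrawn.
- Scrotal ultrasound and SF-36: not linked to the supply trigger, so not protected.

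**Size for a hormone retest.** Protocol 2.3.2 reports a mean fall of 13% in A4 and 17-OHP after 2 weeks at 200 mg/day. Taking that as the shift in an affected placebo subject (an assumption, since placebo subjects move to 100 mg):
- ln(1 − 0.13) = −0.139 per affected subject.
- One of 18: −0.139/18 = −0.008 on the placebo log mean. Three of 18: 3 × (−0.139)/18 = −0.023.

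**A deliberately pessimistic bound on the sample-size scale** (SAP 7: 15 per group, 50-point difference, SD 30).
- Standard error: 30 × √(2/15) = 10.95. Power: Φ(50/10.95 − 1.96) = 0.995, consistent with the plan's statement of at least 80%.
- If m of 15 placebo values carry a fraction g of the effect, the difference is 50 − (m/15) × g × 50.
- m = 1, g = 13/50 = 0.26: 49.1 points, power 0.994.
- m = 3, g = 1: 40.0 points, power 0.955.

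**Share of data for the unprotected endpoints.** The documents do not say how many men per arm will have TARTs. If 3, 5 or 8, one late scan is 33%, 20% or 12.5% of an arm. One late SF-36 among 18 is 5.6%. Nothing in the documents shows how far TART volume or SF-36 would move over one to three weeks on drug, so no bias can be put on these.

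**The case against.** The strongest reply is that this is a fallback that the plan's operations make rare. It applies only when the scheduled value is missing, and the supply trigger means hormone data should nearly always exist before Part B drug does. That stands. It removes most of the risk for the primary analysis and all five secondary analyses, which are on A4 or 17-OHP.

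A reader might infer that the A4 dose response itself is contaminated, or that escalating uncontrolled subjects flatters the low doses. The documents do not support this: escalation after Week 18 is decided from the Week 18 A4 result, so an escalated subject has that value.

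A reader might also extend the point to safety, Week 30 or Week 76. Safety data are summarised by actual treatment (SAP 14, 14.1, 14.2). No listed efficacy endpoint is evaluated at Week 30. For Week 76, SAP 9.3.4 defines completion of treatment as completing that visit, which is flagged first. What remains is a single omitted item: with a last dose at Day 533, the follow-up window (Days 534 to 563) lies inside the Week 76 window (Days 513 to 575).

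It is fair, too, that a generous window has a purpose. Protocol 6.5.1.5 delays draws until 5 to 7 days after return to usual GC dosing following stress dosing, and the primary model uses actual days. That argues against shortening the window by calendar. It does not argue against a cut-off at first Part B dose, because a late Week 18 visit still on Part A drug would be kept.

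**Conclusion.** The gap is real: the stated rule admits values that do not meet the endpoint's own definition, and the SAP has closed the equivalent gap for baseline hormones. Its practical reach is narrow: a make-up scrotal ultrasound, a late SF-36 or a single-analyte retest. TART and SF-36 are exploratory, and SAP 10.5 leaves all secondary and exploratory results without alpha control.

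For one to three affected placebo subjects of 18, the shift in a hormone log mean is about −0.008 to −0.023, assuming the 13% two-week fall applies. TART is where one value could matter most, but only on an assumed small number of men with lesions and an unknown short-term change. The number of affected values cannot be determined from the documents and is probably small. This is worth correcting before lock, mainly so that nobody has to decide after unblinding which late values count. It is not a reason to doubt the primary analysis.

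**What to change.** Add to SAP 9.4 that a value may be assigned to Week 18 only if collected on or before the date of the subject's first Part B dose. The window then ends at the earlier of Day 148 and that date; subjects who never take Part B drug keep Day 148. Later values are treated as missing under each endpoint's stated rule. Apply the condition to all four arms alike. Because drug is taken in the evening, a hormone draw at 8 AM on the date of that dose still qualifies. Derive the date from the Part B supply assigned after A4 confirmation, not from any bridging supply of Part A drug.

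Optionally, state that an off-drug follow-up assessment (last dose +1 to +30) does not fill a missing Week 76 item.

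The cost is one sentence and one derivation condition. A few late values are lost. This bites most for TART, where SAP 13.5.3 does not impute, so an excluded scan removes that man from the Week 18 comparison.
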